This interface will include data on both ICS and SABA inhaler use. The interface will also have flags to notify the office of under or overuse of inhalers, with a protocol in place to reach out to patients. We will also be assessing the factors associated with the feasibility and sustainability of the Remote Health Management Platform by the healthcare team. This will be done by weekly contact with the healthcare team, rapid cycle improvement of the web portal, and written assessments. Follow-up assessments through interview will be conducted at the end of the trial with health providers.

[figure not shown]

Figure 1. Study Arms

Participant Sites

The participant sites will be pediatric clinics in the Chicagoland Area. Each site in this proposed study has a strong history of research collaborations with [name], which includes the ability to recruit and retain patients in research studies.

We will be recruiting from at least four of the following sites:

- Children’s Healthcare Associates
- Chicago Family Asthma and Allergy
- Clark/Deming Resident Clinic (Lurie Children’s)
- Pulmonary Clinic (Lurie Children’s)
- Lurie Children’s Uptown Clinic

Study Design and Procedures

1. **Design:** We will conduct a randomized controlled trial comparing asthma inhaler use and asthma-related outcomes between children who either receive the Remote Health Management Platform (intervention) or Standardized Education (control) for asthma management. We will use a prospective cohort design to determine the effect of the intervention on the aforementioned outcomes.

We will enroll patients from Chicago pediatric clinics, as well as inpatient units at Lurie Children’s Hospital. At enrollment, we will randomize children to either the Remote Health Management Platform (intervention) group or the Standardized Education group (control).

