- b. A member of the research team will go in person to each clinic once per week to ensure that the pilot phase is running smoothly and optimally.
- c. A member of the research team will conduct telephone interviews with these families one week after enrollment. These phone calls will determine how the device is working, if participants foresee any obstacles to the use of the device, and to answer any other questions participants might have.
- d. A member of the research team will reach out to enrolled parents via phone, text, or email once a week (4 times in total) to inquire about how well the device is working, and if this is a feasible Platform to use.
- e. After 30 days, a member of the research team will again conduct interviews to get feedback. This pilot group will continue to use the device for one full year and will assist us with trouble shooting throughout the intervention.

4. Enrollment/Visit 1/Baseline Measurements

Informed online consent will be obtained at the time of enrollment. The consent form will be stored utilizing REDCap, which is a secure, online software. Families in the Intervention arm will receive Remote Health Management sensors. Data collected at the time of enrollment will include the following for each participant:

- c. Basic demographic and clinical history data (obtained by a review of medical records)
 - a. Include: name, date of birth, date of asthma diagnosis, zip code, history of a course of oral corticosteroid, current medications, phone call/email history to the clinic, asthma exacerbation history, and history of asthma-related ED visits and hospitalizations.
- d. Parent questionnaires, including the Asthma Control Test (ACT), Parental Asthma Management Self Efficacy (PAMSE) scale, and the Pediatric Asthma Caregiver's Quality of Life Questionnaire (PACQLQ).

All enrolled children, regardless of study arm, will have allergen testing via ImmunoCAP. This is a simple blood draw that can help further guide the knowledge and overall managements of child's asthma. This will be incorporated into the Remote Health Management software for the intervention group and be disclosed to the control group as well. The volume of the blood to be drawn for the assessment is 1.3 mL of serum or plasma is required to process the allergen panel we intend to use in the study.

5. Daily Inhaler Use Management

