The Remote Health Management team (Propeller Health) utilizes telehealth concepts, including an FDA-approved sensor, mobile apps, predictive analytics, and feedback to help patients and providers better manage asthma.^{11,12} The sensor monitors the use of inhaled medications (ICS and SABA), capturing the date, time, and number of uses. The sensor transmits this information via Bluetooth to a paired smartphone or hub. The location of the event is also securely uploaded to the cloud if the sensor is connected to the Smartphone at the time the sensor is used. Data can be uploaded to the caregiver's smartphone and to the patient's web portal, which their healthcare team will have access to help overall management.¹³

The sensors will be distributed to participants by the study team. We will aim for participants to engage with the study team before going to the clinic or hospital so the device is ready to use at the time of their appointment. This will require the participants to call the research team and the consent being described over the phone to the participants. At their appointment and when the device is given, the participants will sign the consent.

6. Randomization

After recruitment, participants will be stratified by age, sex, and insurance status. They will then be randomly assigned to one of the two study arms.

After recruitment, participants will be stratified by age (4-7 vs 8-17), sex (M vs F), and insurance type (private vs. public), resulting a total of eight strata (stratum1: 4-7, M, Private, stratum2: 4-7, M, Public, stratum3: 4-7, F, Private, etc.). Since this is not a double-blind study and no centralized randomization system will be implemented, one randomization schedule will be generated for each site. Each randomization schedule will contain all eight strata. To ensure balanced treatment allocations within each stratum, 20 randomization blocks will be generated within each stratum. Each block has a block size of 4 with a random permutation of treatments A and B (eg, block 1=AABB, block2=ABBA, etc). Each site's randomization schedule will begin with a distinct randomization sequence number which is different from the subject ID number. For example, site 1's randomization schedule will begin with randomization sequence number 100001, site 2's randomization schedule will begin with randomization sequence number 2000001, etc.

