The site investigator will assign the randomized treatment to a patient in the sequential order, based on the stratum the patient belongs to.

7. Intervention

- a. After enrollment, participants in the Remote Health Management Sensor group will have the full Remote Health Management Sensor Platform (i.e. mobile application, physician access to inhaler use data, etc.). Research staff will review uploaded sensor data on a daily basis. If participants are enrolled into the control group, they will only receive Standard Asthma Education. The Standard Asthma Education follow the NAEPP (National Asthma Education and Prevention Program) guidelines for asthma management. This will include the following list of topics: 1. What is Asthma (Explanation of symptoms); 2. Asthma triggers (what those are and how to avoid them); 3. Using medications (how to use prescribed asthma medications, the difference between controller medications and rescue inhalers, how to appropriately use a spacer, how to appropriately use a mask); and 4. Managing asthma control (purpose of asthma control test and how to complete it, purpose of an asthma action plan and how to read and complete it, how to appropriately use a peak flow meter).

- b. All participants will receive allergen testing, done by their physicians to ascertain their environmental triggers. This will be incorporated into the Remote Health Management software for the intervention group.
- c. If uploaded data reveals elevated SABA use, healthcare team staff will be expected to contact caregivers if needed to ascertain the context of the elevated use and schedule appointments as needed. Information regarding this contact will be documented in the patient's EMR and available to researchers.
- d. The Remote Health Management Platform will send education, based on management plan and identified asthma triggers, to participant in the intervention group.

8. 1 month from start of enrollment

- a. Control Arm- Caregivers will take the ACT, PAMSE, iTRACC survey, and PACQLQ. Caregivers will also be asked about acute exacerbations, ED visits, and hospitalizations as visits to out-of-network healthcare facilities may not be visible in the EMR. This information will be collected via email or phone for both groups utilizing a REDCap survey link for each participant.

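### Section 5 of the protocol ties signed consent to hand-over of an intervention-only device, and no section rules out assignment before signature

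*Protocol*

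**What the plan says.** Protocol section 5 (Daily Inhaler Use Management) aims for families to be in touch with the study team "before going to the clinic or hospital so the device is ready to use at the time of their appointment". It continues: "This will require the participants to call the research team and the consent being described over the phone to the participants". Signature comes later: "At their appointment and when the device is given, the participants will sign the consent".

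Only one arm gets a device. Section 4 (Enrollment/Visit 1/Baseline Measurements) states: "Families in the Intervention arm will receive Remote Health Management sensors". Section 7 (Intervention) states: "If participants are enrolled into the control group, they will only receive Standard Asthma Education".

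Three other places bear on timing:
- Section 4: "Informed online consent will be obtained at the time of enrollment". The baseline questionnaires are collected at the same point.
- Section 1 (Design): "At enrollment, we will randomize children to either" the platform or the education arm.
- Section 6 (Randomization): stratification and assignment follow recruitment. There is no central system, the trial is not double-blind, and the site investigator assigns from the site's own schedule.

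None of these places signature before or after assignment, or baseline questionnaires before or after assignment. Section 1 gives each child a study ID before baseline measurement, but section 6 says the randomisation number is different from that ID, so this does not settle the order.

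**The concern.** Section 5 links the signature to an event that happens in one arm only. A device cannot be given to a family as part of its arm until the arm is settled. If signing happens as the device is given, the arm is settled by the time the family signs.

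Two things are then at risk on the phone route:
- **Refusal that depends on the arm.** A family that knows its arm can decline because of it. Control families, who are offered no device, plausibly have more reason to. An assigned family that never signs leaves no follow-up data. The multiple imputation in the SAP is not set up for such children, and neither document says how they would be counted.
- **Baseline scores given with the arm known.** ACT, PAMSE and PACQLQ are reported by the parent. ACT is a primary outcome, and SAP Aim 1 analyses its change from baseline with the baseline score as a covariate. If assignment comes first, that covariate may already reflect the arm.

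**Working it through.** **Step 1. Order of events.** Two sequences can be built from the text.

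- *Literal section 5:* consent described by phone; device readied; appointment; device given and consent signed together. Because only one arm gets a device, assignment is at or before signature. Other text is consistent with this. Recruitment may start by call or mailing (Study Enrollment), assignment follows recruitment (section 6), and the stratifiers (age, sex, insurance) need no visit. Platform installation is described for the individual family (Study Enrollment), and the sensor works with a paired smartphone (section 5).
- *Single visit:* sign online, randomise, hand over a sensor from prepared stock. This fits the Design section, section 4 and the statement in section 1 that devices are given at the enrollment visit.

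No sentence chooses between them.

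**Step 2. The plan's own sample size.** Inputs from Sample Size Determination: rates 0.545 and 0.75, two-sided alpha 0.05, power 85%, drop-out 20%.

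- OR = (0.545/0.455)/(0.75/0.25) = 0.3993; log OR = -0.9181.
- n per arm = (1.960 + 1.036)² × [1/(0.545×0.455) + 1/(0.75×0.25)] / 0.9181² = 99.76, rounded up to 100.
- 100/0.80 = 125 per arm, 250 in total.

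The stated 250 is reproduced. Reordering consent and assignment does not alter it.

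**Step 3. Illustration of size.** The documents give no refusal rate, refuser event rate or phone-route share, so all three are assumed. Let s be the phone-route share, d the refusal among phone-route controls (none in the intervention arm, no replacement), f = s×d, and r the refusers' event rate. The observed control rate is (0.75 − f×r)/(1 − f). With r = 0.60 or 0.90 the shift is ±0.15×f/(1 − f).

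| d | s = 1: shift (share of 0.205) | s = 0.5: shift (share of 0.205) |
|---|---|---|
| 5% | 0.008 (4%) | 0.004 (2%) |
| 10% | 0.017 (8%) | 0.008 (4%) |
| 15% | 0.026 (13%) | 0.012 (6%) |

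The planned difference is 0.75 − 0.545 = 0.205. For example, with s = 1, d = 15% and r = 0.60: (0.75 − 0.09)/0.85 = 0.776. With r = 0.90: (0.75 − 0.135)/0.85 = 0.724. The direction depends on who refuses: low-risk refusers raise the observed control rate and flatter the intervention, and high-risk refusers do the opposite.

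**Step 4. A wider range, with no true effect.** Take risk 0.75 in both arms, r from 0.5 to 1.0, 100 evaluable intervention children and 100×(1 − f) evaluable controls, with a Wald test on the log OR.

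- f = 10% of all controls: observed control rate 0.778 to 0.722; spurious OR 0.86 to 1.15; two-sided type I error up to about 7%.
- f = 20% of all controls: observed control rate 0.812 to 0.688; spurious OR 0.69 to 1.36; type I error up to about 17%.

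If half the families came by phone, these need refusal of 20% and 40% among phone-route controls.

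Loss of numbers matters less. With the planned rates, power falls from 85.1% to 82.9% at f = 10% and 80.1% at f = 20%.

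Steps 3 and 4 use the binary exacerbation rate from the sample size section. The planned analyses are of counts and of ACT change, so these results indicate scale only.

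**The case against.** The strongest reply is that the single-visit reading is compatible with every section. Consent is only described by phone. Nothing says that a family is told its arm on the call, or that a device is set up for a named child because of assignment; a device could be readied for every family that calls. Section 5 states an aim, concerns sensor logistics, and covers one route among several, since families may also be recruited in clinic or on the inpatient service. This stands, and it limits the point to an order that the protocol leaves open.

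A reader might infer three stronger things:
- *That the arm is fixed and known before written consent.* This needs an allocation step before the appointment, which no section states.
- *That control families have no point at which to sign.* Section 4 places consent at enrollment without limiting it to one arm.
- *That the protection of randomisation is lost.* With an unknown phone-route share, unknown refusal and unknown direction, the documents support only that it may be compromised on that route.

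It is also fair that the consent form and some pages after Study Enrollment are not in the text examined here. If they state an order, section 5 should be brought into line with it.

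What does not stand is that this is merely missing detail. Section 5 gives a positive instruction, and following it literally puts assignment at or before signature.

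**Conclusion.** The point holds as an unresolved order with a literal reading that is unsafe. On the phone route, section 5 places assignment at or before signature, and the Design section, section 4 and section 6 do not exclude this. Arm-dependent refusal, and parent-reported baselines given with the arm known, are therefore possible. The documents do not show that either would occur.

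The size is unknown. Under the assumed 5 to 15% refusal among phone-route controls, the control rate shifts by 0.004 to 0.012 if half the families use that route and by 0.008 to 0.026 if all do. That is 2 to 13% of the planned difference, in either direction. These figures rest on assumed refusal, no replacement and refuser rates of 0.60 or 0.90. They apply only to phone-route families. The point should be corrected because prevention is cheap and later repair in the analysis is not possible; it does not by itself invalidate the design.

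**What to change.** Replace the signing sentence in section 5, and reconcile the Design section, section 4 and section 6, with one sequence for both arms and every recruitment route:

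1. Consent discussed, by phone or in person.
2. REDCap consent signed, remotely or at the visit.
3. Baseline questionnaires completed.
4. Assignment opened.
5. Device set-up (intervention arm) and education (both arms).

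State that no assignment is opened or disclosed before the REDCap consent timestamp, and that every randomised child is counted in the arm assigned.

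**Cost.** The sample size is unchanged and REDCap consent is already planned. Signing remotely before the appointment would change the consent procedure in section 5, so it is more than an edit of words for sites that take that option; signing at the visit avoids this. The practical downside is that some devices will be set up at or after the appointment rather than being ready beforehand. Study Enrollment already describes telephone set-up for families recruited in clinic, and this could be extended to others.

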Children in the Standardized Education group will receive education about NAEPP guideline-based asthma management, including asthma action plans and appropriate and effective inhaler use. During the initial visit, the child participants will get ImmunoCAP allergen testing to ascertain their environmental allergens. This is a simple blood draw that can help further guide the knowledge and overall management of the child’s asthma. Allergen testing is not mandatory to participate in this study. They will also receive education on the benefits of an active lifestyle on asthma control and other health outcomes, appropriate physical activity types for asthma control (e.g., aerobic, moderate-intensity physical activities), setting goals for physical activity (e.g., daily step counts, one-hour of moderate-intensity physical activity per day), and recommendations for self-monitoring physical activity levels.

At the enrollment visit, children in the intervention group and their families will receive all devices and software needed to track inhaler use and physical activity, as well as the education that the Standardized Education group receives. The Remote Health Management sensor will be enabled so that both caregivers and healthcare team will be able to track the child participants' inhaler use. The software platform will provide participant families with tailored educational material via a mobile device-based app. A research assistant will provide the education on how to use the sensor device and the app, as well as the standardized education as described above. The child participants will also obtain allergen testing via ImmunoCAP.

All participants will be assigned a study ID number prior to the collection of baseline measurements. Data will be de-identified and linked only by their study ID number. Data from the sensor will be uploaded to a cloud-based storage facility for analysis.

2. Inclusion Criteria:

- a. English-speaking parents of:
 - i. Children 4-17 years of age. Using both NHLBI (National Heart, Lung, and Blood Institute) guidelines and based off of a physician expert panel, the research team has limited the ages to 4-17 years old. It has been shown to be difficult to properly diagnose individuals less than 4 years of age with asthma. Usually, they are diagnosed with reactive airway disease or bronchial virus.

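### Section 6 has the site investigator assign open-label treatment in order from a local schedule in fixed blocks of four, and the visible text describes no step that conceals the next assignment

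*Protocol*

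**What the plan says.** **Allocation.** Protocol section 6 (Randomization) stratifies by age (4-7 or 8-17), sex and insurance type, giving eight strata at each site. On the mechanism it says: "Since this is not a double-blind study and no centralized randomization system will be implemented, one randomization schedule will be generated for each site". On the blocks: "Each block has a block size of 4 with a random permutation of treatments A and B", with 20 blocks per stratum. On who assigns: "The site investigator will assign the randomized treatment to a patient in the sequential order, based on the stratum the patient belongs to". The SAP says nothing about allocation. Appendix 4 is titled as the randomization schedule, but only the title can be seen.

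**Who finds and enrols families.** Under Study Enrollment, the healthcare team identifies candidates and a research assistant (RA) recruits them. The inclusion criteria have a trained RA identify children with moderate-to-severe asthma. No section says who holds the schedule, who may see it, or how an assignment is revealed.

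**Timing.** The Design paragraph randomizes at enrollment. Section 6 puts it after recruitment: "They will then be randomly assigned to one of the two study arms". Study Design and Procedures adds: "At the enrollment visit, children in the intervention group and their families will receive all devices and software needed to track inhaler use". Section 4 makes the enrollment visit the baseline visit. It collects the parent-reported ACT, PAMSE and PACQLQ there and mentions intervention families receiving sensors in the same paragraph. On consent, section 4 says: "Informed online consent will be obtained at the time of enrollment". Section 5 instead has consent signed at the appointment when the device is handed over, and aims for the device to be ready by then.

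**The concern.** Section 6 offers the lack of blinding as a reason for doing without a central system. Blinding after assignment and concealment before it are separate safeguards. An open-label trial needs the second at least as much, because past assignments are visible to site staff and help predict the next one.

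If the coming arm can be foreseen, it can influence which families are approached, or when they are entered. The people who identify and recruit families have discretion over both. Any resulting imbalance would reach all four primary outcomes (ACT, hospitalizations, ED visits, oral corticosteroid use). The Aim 1 models can adjust for measured baseline differences but cannot fully repair selection on unmeasured ones.

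The unstated order of baseline and randomization is a smaller matter. Baseline ACT is parent-reported and is a covariate in the Aim 1 model for change in ACT. If parents knew the arm when answering, and that knowledge moved answers differently in the two arms, the adjusted treatment effect would be biased.

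**Working it through.** **Inputs.** Block size 4, two per arm; eight strata per site; one schedule per site (all section 6). At least four of five listed sites (Participant Sites). Total 250 children (Sample Size Determination).

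**The plan's own figure.** The documents give no figure for predictability. The 250 is used here only to size the cells. It reproduces from a Wald test on the log odds ratio: n per arm = (1.960 + 1.036)² × [1/(0.545 × 0.455) + 1/(0.75 × 0.25)] / 0.918² = 99.8. That is 199.5 in total, and 199.5/0.80 = 249.4.

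**With sight of the list.** Every upcoming allocation is known.

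**Without the list.** Suppose someone knows the block size, remembers every earlier allocation in the same site-by-stratum cell, and always guesses the arm with more places left in the block. The six orderings of AABB are equally likely, so:

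| Place in block | Probability the next arm is certain | Probability the best guess is right |
|---|---|---|
| 1 | 0 | 1/2 |
| 2 | 0 | 2/3 |
| 3 | 1/3 (first two alike) | 1/3 × 1 + 2/3 × 1/2 = 2/3 |
| 4 | 1 | 1 |
| Sum | 4/3 | 17/6 |

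For a cell of n children, add up the places used and divide by n:

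| n | Certain | Guessed correctly |
|---|---|---|
| 4 | (4/3)/4 = 33.3% | (17/6)/4 = 70.8% |
| 5 | (4/3)/5 = 26.7% | (17/6 + 1/2)/5 = 66.7% |
| 6 | (4/3)/6 = 22.2% | (17/6 + 1/2 + 2/3)/6 = 66.7% |
| 7 | (4/3 + 1/3)/7 = 23.8% | (17/6 + 1/2 + 2/3 + 2/3)/7 = 66.7% |
| 8 | (8/3)/8 = 33.3% | (17/3)/8 = 70.8% |

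Fully concealed allocation would give 0% and 50%. Complete blocks give the ceiling, 33.3% and 70.8%, whatever the cell size.

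**Why 4 to 8 per cell.** An even spread gives 250/(5 × 8) = 6.25 or 250/(4 × 8) = 7.8 children per cell. The documents do not give the real spread. Simulating 250 children with equal cell probabilities gave about 27% certain and 68% guessed for 40 cells, and about 28% and 68% for 32 cells. Over 24 assumed uneven spreads (4-5 sites, site shares 5-50%, 30-50% aged 4-7, 50-85% public insurance) the averages were 26.6-28.6% certain and 67.8-68.7% guessed.

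**Order of events.** The only event placed before the baseline measurements is assignment of the study ID (Study Design and Procedures). Section 6 says the randomization sequence number is a different number, so that statement does not date randomization. The Design paragraph and sections 4, 5 and 6 are each compatible with more than one order. Sections 4 and 5 also differ on when and how consent is given.

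**The case against.** **Recruiting and assigning are different roles.** An RA recruits and the site investigator assigns, and no text says the RA sees the schedule. This stands as far as it goes. It is not concealment: no text keeps the schedule from the RA or the healthcare team, and the investigator may belong to the team that identifies candidates.

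**A procedure may exist in text not seen.** Appendix 4 is unseen, and so are some pages after Study Enrollment. This stands. A reader might infer that the trial has no concealment at all. The documents support only that none is described in the visible text.

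**The guessing figures are generous to the guesser.** They assume perfect recall over about a year of enrollment and optimal play. This stands, so they are upper bounds for someone without the list.

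**The timing evidence is thin.** A reader might infer that families learn their arm before consenting or answering the baseline questionnaires. Only section 5, with a device ready by the appointment and consent signed when it is given, leans that way. Set-up by telephone under Study Enrollment follows recruitment in clinic, so it does not suggest early knowledge. Section 4 precedes section 6, and the closing Timeline lists collection of past EMR data before randomization. None of this fixes when the questionnaires are answered, but it makes the worrying order less natural.

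**Conclusion.** The concern holds for concealment. Followed as written, section 6 lets upcoming allocations be foreseen: completely by anyone with the list, and for at most about 22-33% with certainty and 67-71% by best guess for someone who only tracks past assignments, with 4 to 8 children per cell. The cell sizes are an assumption about how 250 children spread over sites and strata. That the site investigator knows the arm is inferred from the open-label design and the visible sensor.

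A reader might take these percentages as a measure of bias, or as evidence that enrolment would be steered. The documents support neither. The figures measure predictability only.

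The order of baseline and randomization is a point to clarify, not a demonstrated flaw. A reader might want to put a size on the resulting ACT bias. The documents give neither the slope on baseline nor any shift in answers between arms, and bias arises only if there is such a differential shift, so no size is claimed.

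**What to change.** Amend section 6 so that each assignment comes from a concealed mechanism. One option is REDCap, already used for surveys and for consent: "The consent form will be stored utilizing REDCap, which is a secure, online software". The documents do not show it used for allocation, so this depends on whether it can be extended. The other option is sequentially numbered opaque sealed envelopes prepared by the central team, which needs no central computer system.

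Under either option:
- Reveal the arm only after signed consent, confirmed eligibility and irrevocable entry.
- Keep the list and the block size from anyone who identifies or enrols families, including in any protocol copy or appendix that sites receive.
- State what Appendix 4 contains and who sees it.

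In the same amendment, reconcile the Design paragraph and sections 4, 5 and 6 to one order: consent and the baseline ACT, PAMSE and PACQLQ first, then randomization, then device hand-over.

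The cost is a short amendment, one allocation set-up, and some loss of the pre-visit device readiness that section 5 aims for. Sample size is unchanged.
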